### **9.7.3      *Columbia-Suicide Severity Rating Scale***

The number and proportion of subjects with each C-SSRS item (suicidality, suicidal ideation, suicidal behavior, completed suicide, emergence of suicidal ideation, emergence

of serious suicidal ideation, worsening of suicidal ideation, and emergence of suicidal behavior) at each time point will be determined.

The definition for each C-SSRS item other than completed suicide is provided as follows:

- Suicidality: “Yes” to any question of suicidal ideation or suicidal behavior
- Suicidal ideation: “Yes” to any question of suicidal ideation
- Suicidal behavior: “Yes” to any question of suicidal behavior
- Emergence of suicidal ideation: Suicidal ideation is absent at baseline and present after baseline.
- Emergence of serious suicidal ideation: Suicidal ideation is absent at baseline and present with an intensity of 4 or 5 after baseline.
- Worsening of suicidal ideation: Increase in the intensity of suicidal ideation after baseline
- Emergence of suicidal behavior: Suicidal behavior is absent at baseline and present after baseline.

The baseline in this section is the baseline specified in [Section 9](#), not the assessment performed using the “Baseline/Screening Version.” If the response to all the questions on suicidal ideation is negative, the intensity of suicidal ideation will be 0.

The categories of suicidal ideation and suicidal behavior are indicated below.

Suicidal ideation:

1. Wish to be dead
2. Non-specific active suicidal thoughts
3. Active suicidal ideation with any methods (not plan) without intent to act
4. Active suicidal ideation with some intent to act, without specific plan
5. Active suicidal ideation with specific plan and intent

Suicidal behavior:

Actual attempt, interrupted attempt, aborted attempt, preparatory acts or behavior, suicidal behavior

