**Table 1.3-1 Schedule of Assessments**

	Screening Period	IMP Administration Period												Washout e
		Period 1 Baseline Examination		Period 1 (Administration of QW Formulation 48 mg in a Fasting or Fed State)										
Day (per treatment period)	From -42	-1		1		2		3	4	6	8	11	14	
Hours predose/postdose	—	-24	-2	0	3	9	24	36	48	72	120	168	240	312
Vital signs (body temperature, pulse rate, blood pressure) k	×		×			×	×		×	×		×		×
Body weight	×	×										×		×
12-Lead ECG k	×	× l				×	×		×			×		×
DIEPSS			×						×			×		×
C-SSRS	×	×					×		×	×	×	×	×	×
CGI-S			×									×		×
CGI-I												×		×
Adverse events	◀													
Concomitant medications/therapies	◀													
Bowel-movement investigation m	◀									▶				◀
Hospitalization period	Outpatient visits permitted	Hospitalization										Outpatient visits permitted		

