#### **2) Methods**

The investigator or designated person will perform the C-SSRS assessment at the scheduled time points. The C-SSRS assesses the occurrence, severity, and frequency of suicidal ideation/behavior during the assessment period. This assessment consists of the “Baseline/Screening Version,” which assesses the history of suicide-related events and suicidal ideation in the lifetime and within the last 24 months, and the “Since Last Visit Version,” which focuses on suicidality since the last assessment in the trial. The “Baseline/Screening Version” will be used at screening and the “Since Last Visit” will be used at subsequent time points for C-SSRS assessment. Whether or not assessment is performed and the date and time of assessment, and the assessment results will be recorded in the source documents and the eCRF. As far as possible, the same assessor will perform assessment of the same subject throughout the trial period.

The presence of suicidal ideation 1 to 2 will be assessed with “yes” or “no,” and if the answer to 2 is “yes,” suicidal ideation 3 to 5 will be assessed. If the answer to suicidal ideation 1 or 2 is “yes,” the intensity of ideation will also be rated. Intensity of ideation will be rated on a 5-point scale for frequency and duration and a 6-point scale for controllability, deterrents, and reasons for ideation.

The following suicidal behavior will also be assessed with “yes” or “no,” and if the answer is “yes,” details will be assessed, and the total numbers of each suicide attempt will be recorded.

If there is an actual attempt, actual lethality/physical damage will be rated on a 6-point scale, and if actual lethality/physical damage is 0, potential lethality will be rated on a 3-point scale.

Suicidal ideation:

1. Wish to be dead
2. Non-specific active suicidal thoughts
3. Active suicidal ideation with any methods (not plan) without intent to act
4. Active suicidal ideation with some intent to act, without specific plan
5. Active suicidal ideation with specific plan and intent

Suicidal behavior:

Actual attempt, non-suicidal self-injurious behavior, interrupted attempt

Aborted attempt, preparatory acts or behavior, suicidal behavior, suicide (only for “Since Last Visit Version”)

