### **9 Safety Analyses**

The safety analysis set will be used for analysis by meal condition (in subjects who receive trial treatment under each meal condition). The baseline value will be the last measurement prior to IMP administration in each period.

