#### **9.2 Adverse Events**

Adverse events will be coded using Medical Dictionary for Regulatory Activities (MedDRA) Ver. 27.1. The incidence of the following events will be summarized by system organ class (SOC) and preferred term (PT). If an AE occurs more than once in the same subject in the same period, the most severe event will be used in summarization.

- Treatment-emergent AEs (TEAEs)
- TEAEs by severity
- TEAEs with an outcome of death
- Serious TEAEs

A TEAE in each period is defined as a TEAE that occurs after IMP administration in each period up to before IMP administration in the next period (if the IMP is to be administered in the next period).

Similarly, IMP-related TEAEs will also be summarized.

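### Suicidality first arising between the Period 1 Day 14 C-SSRS and the Period 2 Day -1 C-SSRS is used only as the Period 2 baseline: it is not tabulated as emergent for Period 1, and it blocks emergence in Period 2

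*SAP*

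**What the plan says.** Protocol 8.7.5 uses the Baseline/Screening version of the C-SSRS once, at screening. The Since Last Visit version, "which focuses on suicidality since the last assessment in the trial", "will be used at subsequent time points for C-SSRS assessment".

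SAP 9 sets one baseline rule for all safety data: "The baseline value will be the last measurement prior to IMP administration in each period". SAP 9.7.3 applies that rule to the C-SSRS and says the baseline is "not the assessment performed using the" Baseline/Screening version. Emergence is then defined as "Emergence of suicidal ideation: Suicidal ideation is absent at baseline and present after baseline", with the same form for suicidal behavior. The items are counted by time point: "emergence of suicidal behavior) at each time point will be determined".

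SAP 3.4 leaves withdrawal, follow-up and unscheduled data out of by-time-point summaries. Its exception, which brings back withdrawal and unscheduled data, covers the potentially clinically significant (PCS) criteria and the QTcF categories. It does not cover the C-SSRS.

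For adverse events, SAP 9.2 assigns to a period whatever "occurs after IMP administration in each period up to before IMP administration in the next period". SAP 9.3, 9.4, 9.6 and 9.7.1 use the same window for the PCS laboratory, vital-sign, ECG and weight counts. SAP 9.7.3 has no such sentence.

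**The concern.** A Since Last Visit rating describes an interval, not the subject's state on the day. In Period 1 this does no harm: the Day -1 rating looks back to screening, before any IMP. In Period 2 the same rule takes as its pre-dose reference a rating whose look-back lies entirely after the Period 1 dose.

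Two results follow for suicidality that first arises in that interval. It is not shown as emergent or worsening under the Period 1 meal condition, although it followed that dose. It also makes the Period 2 baseline positive, so a recurrence after the Period 2 dose cannot count as emergent. Table CT-15 and the adverse-event tables could then disagree about the same event. The C-SSRS is a named safety endpoint, and CT-15 is its only summary table in the SAP's table list.

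**Working it through.** The plan states no figure to reproduce. The check is calendar arithmetic and a trace of the definitions.

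**Inputs**
- Protocol "Table 1.3-1 Schedule of Assessments": Period 1 C-SSRS at screening, -24 h, then 24, 48, 72, 120, 168, 240 and 312 h. That is seven post-dose ratings, with none in the washout column. Period 2 has a baseline rating on Day -1.
- Protocol Table 1.3-1, footnote c: Period 2 dosing can be moved between Day 30 and Day 36, counting the Period 1 dose as Day 1.
- Protocol Table 1.3-2: the 312 h visit has a window of ±24 hours.
- Protocol 1.3.2.4: if Period 2 dosing is postponed, the Day -1 assessments are repeated.

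**Length of the look-back**
- Day 14 is (14 - 1) × 24 = 312 h, which agrees with the table.
- Look-back of the Period 2 baseline = (Period 2 dose day - 1) - 14.
- Dose on Day 30: 29 - 14 = 15 days. Dose on Day 36: 35 - 14 = 21 days. With the ±24 h window on the Day 14 visit, the range is 14 to 22 days.
- As a share of the time between doses: 15/29 = 52% and 21/35 = 60%. These are shares of calendar time, not of events.
- If the unadjusted Period 2 dose day is Day 29 (an assumption, made because 29 + 28 days of follow-up = 57, the stated length of the IMP administration period), the look-back is 28 - 14 = 14 days, or 14/28 = 50%.

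**Trace of one subject**
1. Ideation is absent at Period 1 Day -1 and at all seven post-dose ratings. Nothing is emergent in Period 1, correctly so far.
2. Ideation first occurs after Day 14 and is recorded on Period 2 Day -1. That rating is not a Period 1 time point, so Period 1 gets no emergent or worsening entry.
3. The same rating is the last one before the Period 2 dose, so ideation is present at the Period 2 baseline.
4. Ideation recurs at the same intensity at 72 h in Period 2. It is not emergent, because baseline is positive, and not worsening, because intensity has not risen.
5. If it recurs at intensity 4 or 5 above a lower positive baseline, it counts as worsening. It still cannot count as emergence of serious ideation, which also requires absence at baseline.
6. If the event in step 2 is reported as an adverse event, SAP 9.2 makes it a TEAE of Period 1.

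**Postponed dosing.** If a Day -1 rating has been done and is then repeated, the final baseline may look back only to the first Day -1 rating. An interval event recorded at the first rating then need not block Period 2 emergence, but it still has no Period 1 row.

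**The case against.** The best defense is that CT-15 is a descriptive by-time-point table that ends at Day 14 in both periods. SAP 3.4 keeps follow-up data out of such summaries, so Period 2 is cut off in the same way. Other by-time-point safety summaries use the same per-period baseline. SAP 9.7.3 also sets no end to the time after baseline, so it does not expressly bar the Period 2 Day -1 rating from counting for Period 1. The trial is small (36 completers planned), and recent serious ideation or suicidal behavior excludes a patient at entry.

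Much of this stands. Stopping both periods at Day 14 is a legitimate choice for a by-time-point table, and few events may occur. But the interval data are not merely left out of Period 1: they become the reference for Period 2. A laboratory value or a weight measures the subject on the day, so the per-period baseline suits it; a Since Last Visit rating does not. If the SAP meant the Day -1 rating to count for Period 1, it needs a sentence saying so.

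A reader might infer more than the documents support:
- **That the Period 2 baseline covers all the time since the Period 1 dose.** It reaches back only to Day 14. The first 13 days are rated seven times and compared with the Period 1 baseline.
- **That interval events are never counted.** The ratings appear in listings PDATA-11.1 to PDATA-11.3, reported adverse events are Period 1 TEAEs, and a rise above the Period 2 baseline is still worsening.
- **That every subject entering Period 2 is affected.** Only suicidality first arising in the interval matters, and a repeated Day -1 rating shortens the look-back.
- **That CT-15 assigns the event to the wrong meal condition.** That would need a baseline row in CT-15, and no table shell is shown. A value labelled as pre-dose is in any case not attributed to the dose that follows.

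**Conclusion.** The point holds in this limited form and should be corrected. For suicidality first arising after the Period 1 Day 14 rating and recorded on Period 2 Day -1, the stated rules leave emergence and worsening untabulated for Period 1 and rule out emergence in Period 2. They also conflict with the up-to-next-dose rule used for TEAEs and the PCS counts.

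The exposed interval is 15 to 21 days for Period 2 dosing on Day 30 to 36. This assumes that the Day 14 rating was done on its nominal day, that the Day -1 rating was not repeated, and that CT-15 is built as SAP 9.7.3 reads. The documents give no event rate, so the number of misclassified subjects cannot be estimated and may be zero. The primary pharmacokinetic analysis is not touched.

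**What to change.** In SAP 9.7.3:

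1. Add an any-time-in-period count for each emergence and worsening item, by meal condition, running from IMP administration up to the next period's IMP administration.
2. For Period 1, include every pre-dose Since Last Visit rating of Period 2, including a first Day -1 rating that is later repeated, and compare it with the Period 1 baseline.
3. For Period 2, include withdrawal, unscheduled and any follow-up ratings, and amend the SAP 3.4 exclusion for this count. Extending Period 1 alone would give the two periods unequal windows. With follow-up at 28 days (+7) after the last dose, Period 2 would run about 28 to 35 days, against 29 to 35 days between doses for Period 1.
4. Keep the by-time-point table to Day 14 as it is.
5. For subjects whose Period 2 baseline is positive only because of the interval after Day 14, also report Period 2 emergence against the Period 1 baseline, flagged as a recurrence.

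The cost is SAP wording and a few more rows in CT-15, with no new data collection. The drawback is that some late Period 1 events will fall at low drug exposure; the unchanged Day 14 table keeps the earlier window visible.

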## 10 Pharmacokinetic Analyses

Pharmacokinetic parameters will be calculated in subjects who received at least one dose of the brexpiprazole QW formulation and had at least one plasma drug concentration measurement. The analyses described in [Section 10.1 2\)](#) and [Section 10.2 2\)](#) will be performed on the food effect analysis set.

## 10.1 Statistical Analyses of Primary Pharmacokinetic Endpoints

### 1) Endpoint

Geometric mean ratio and two-sided 90% confidence interval of  $C_{max}$ ,  $AUC_{\infty}$ , and  $AUC_t$  of brexpiprazole in plasma after administration in a fed state versus administration in a fasting state

### 2) Statistical Analysis Methods

The natural log-transformed  $C_{max}$ ,  $AUC_{\infty}$ , and  $AUC_t$  of brexpiprazole in plasma will be analyzed using a linear mixed-effects model with group (fasting-state-administration-first group or fed-state-administration-first group), meal condition (fasting or fed), and period (Period 1, Period 2) as fixed effects, and within-group subjects as a random effect, and the differences in means of natural log-transformed values between meal conditions (fed-state administration – fasting-state administration) and their two-sided 90% confidence intervals will be calculated. The differences in the mean natural log-transformed values (fed-state administration – fasting-state administration) and their two-sided 90% confidence intervals will be inverse-transformed to calculate the ratio of geometric mean values (fed-state administration/fasting-state administration) and two-sided 90% confidence interval. The Kenward-Roger method will be used for approximation of the degrees of freedom.

## 10.2 Statistical Analyses of Secondary Pharmacokinetic Endpoints

### 1) Endpoints

- a) Plasma concentrations of brexpiprazole and metabolite [REDACTED]
- b)  $C_{max}$ ,  $AUC_{\infty}$ ,  $AUC_t$ ,  $t_{max}$ ,  $t_{1/2,z}$ ,  $CL/F$ ,a  $CL/F/BW$ ,a  $t_{last}$ ,  $AUC\%_{Extrap}$ , and  $\lambda_z$  of brexpiprazole and metabolite [REDACTED] in plasma
- c) Ratios of the AUC ( $AUC_{\infty}$  and  $AUC_t$ ) of metabolite [REDACTED] to that of brexpiprazole

### 2) Statistical Analysis Methods

Descriptive statistics will be calculated as described below. However, if more than half of the subjects in an analysis set are excluded from summarization due to missing values, not calculable, or rejected data, descriptive statistics to be calculated for that parameter will include only the number of subjects in the analysis set and the number of subjects tabulated.

- a) Plasma drug concentration
  - For 1) a), descriptive statistics will be calculated at each blood sampling time point excluding the withdrawal and unscheduled time points by meal condition and compound.
  - The descriptive statistics to be calculated will include the number of subjects in the analysis set, the number of subjects tabulated, arithmetic mean, standard deviation, coefficient of variation, minimum, median, and maximum.
- b) Plasma PK parameters (except for  $\lambda_z$ )
  - For 1) b), descriptive statistics will be calculated by meal condition and compound.
  - For 1) c), descriptive statistics will be calculated by meal condition.
  - The descriptive statistics to be calculated will include the number of subjects in the analysis set, the number of subjects tabulated, arithmetic mean, standard deviation, coefficient of variation, geometric mean, minimum, median, and maximum. However, descriptive statistics to be calculated for  $t_{max}$  and  $t_{last}$  will be the number of subjects in the analysis set, the number of subjects tabulated, minimum, median, and maximum.

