Predose	Blood sampling for plasma drug concentration measurement, physical examination, vital signs: within 2 hours predose Other: within 24 hours predose
3 hours postdose	±30 minutes
9 hours postdose	±30 minutes 12-lead ECG only: ±60 minutes
24, 36, 48, 72, and 120 hours postdose	±2 hours
168 hours postdose	±4 hours
240 and 312 hours postdose	±24 hours
Follow-up examination	+7 days at maximum

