CT-10.3	Shift Tables of Clinical Laboratory Test Results - Qualitative Urinalysis (Safety Analysis Set)
CT-10.4.1	Incidence of Potentially Clinically Significant Abnormalities in Laboratory Tests (Safety Analysis Set)
CT-10.4.2	Listing of Potentially Clinically Significant Abnormalities in Laboratory Tests (Safety Analysis Set)
CT-10.5.1	Incidence of Hy's Law Cases (Safety Analysis Set)
CT-10.5.2	Listing of Hy's Law Cases (Safety Analysis Set)
CT-11.1	Descriptive Statistics for Vital Signs (Safety Analysis Set)
CT-11.2.1	Incidence of Potentially Clinically Significant Abnormalities in Vital Signs (Safety Analysis Set)

[figure not shown]
CT-11.2.2	Listing of Potentially Clinically Significant Abnormalities in Vital Signs (Safety Analysis Set)
CT-12.1	Descriptive Statistics for 12-Lead ECG Parameters (Safety Analysis Set)
CT-12.2	Shift Table of 12-Lead ECG Findings (Safety Analysis Set)
CT-12.3	Incidence of Categorical Changes in 12-Lead ECG - QTcF (Safety Analysis Set)
CT-12.4.1	Incidence of Potentially Clinically Significant Abnormalities in ECG Evaluations (Safety Analysis Set)
CT-12.4.2	Listing of Potentially Clinically Significant Abnormalities in ECG Evaluations (Safety Analysis Set)
CT-13.1	Descriptive Statistics for Body Weight and BMI (Safety Analysis Set)
CT-13.2.1	Incidence of Potentially Clinically Significant Abnormalities in Body Weight (Safety Analysis Set)
CT-13.2.2	Listing of Potentially Clinically Significant Abnormalities in Body Weight (Safety Analysis Set)
CT-14	Descriptive Statistics for DIEPSS (Safety Analysis Set)
CT-15	Summary of Suicidality in C-SSRS (Safety Analysis Set)
CT-16.1	Listing of Subjects whose CGI-S has Worsened (Safety Analysis Set)
CT-16.2	Listing of Subjects whose CGI-I has Worsened (Safety Analysis Set)
PKT-1.1	Individual and Summarized Brexpiprazole Plasma Concentrations Following Single Oral Administration of Brexpiprazole QW Formulation (Food Effect Analysis Set)
PKT-1.2	[REDACTED]
PKT-2.1	Individual and Summarized Brexpiprazole Plasma Pharmacokinetic Parameters Following Single Oral Administration of Brexpiprazole QW Formulation (Food Effect Analysis Set)
PKT-2.2	[REDACTED]
PKT-3	Summary of Geometric Mean Ratio with Two-sided 90%CI for Brexpiprazole Pharmacokinetic Parameters (Food Effect Analysis Set)
PKF-1.1	Mean Brexpiprazole Plasma Concentrations Following Single Oral Administration of Brexpiprazole QW Formulation (Food Effect Analysis Set)
PKF-1.2	[REDACTED]

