PKF-2.1	Median Brexpiprazole Plasma Concentrations Following Single Oral Administration of Brexpiprazole QW Formulation (Food Effect Analysis Set)
PKF-2.2	[REDACTED]
PKF-3.1	Individual Brexpiprazole Plasma Concentrations Following Single Oral Administration of Brexpiprazole QW Formulation (Food Effect Analysis Set)
PKF-3.2	[REDACTED]
PKF-4.1	Individual Brexpiprazole Plasma Concentrations Following Single Oral Administration of Brexpiprazole QW Formulation for Test Group in Comparison to Reference Group
PKF-4.2	[REDACTED]

[figure not shown]

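### No within-subject fed-minus-fasting estimate or interval for tmax is pre-specified in the readable text, and two medians read off a coarse sampling grid may hide or exaggerate a shift

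*SAP*

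**What the plan says.** SAP 10.2 1) b) and Protocol 9.4.3.2.2 list tmax, for brexpiprazole and a metabolite, among the secondary PK endpoints. Both documents then give the same summary rule: "For 1) b), descriptive statistics will be calculated by meal condition and compound". For tmax and tlast, the statistics "will be the number of subjects in the analysis set, the number of subjects tabulated, minimum, median, and maximum".

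SAP 10.1 2) treats the primary parameters differently. Log Cmax, AUC∞ and AUCt of brexpiprazole enter a mixed model with group, meal condition and period. The fed-minus-fasting differences are estimated and "their two-sided 90% confidence intervals will be calculated". The output is PKT-3 in SAP Appendix 4, "Summary of Geometric Mean Ratio with Two-sided 90%CI for Brexpiprazole Pharmacokinetic Parameters".

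Two other planned outputs bear on tmax. PKT-2.1 prints individual as well as summarised PK parameters. PKF-4.1 is titled "Individual Brexpiprazole Plasma Concentrations Following Single Oral Administration of Brexpiprazole QW Formulation for Test Group in Comparison to Reference Group". Neither provides an estimate of the shift.

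**The concern.** The objective is the effect of food on the PK of a once-weekly oral product. A meal can move the peak later without moving Cmax or AUC much, and the ratios in PKT-3 do not measure that. tmax is the listed endpoint closest to the question. Each completer supplies one fed and one fasting value, but the planned summary describes the two conditions separately, with neither pairing nor period adjustment.

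Sampled tmax can also take only a few values. The gaps between scheduled postdose times are 6, 15, 12, 12, 24, 48, 48, 72 and 72 h. A median on such a grid either stays put or jumps a step, and may do either for reasons unrelated to the size of the within-subject shift. At stake is whether the report can state the delay, with its uncertainty, by a method fixed in advance.

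**Working it through.** **Inputs from the documents.** Postdose sampling times: Protocol Tables 1.3-1 and 1.3-2. 36 completers: SAP 3.1. 1:1 allocation: Protocol 6.1.2, hence 18 per sequence if completion is even. The documents give no figure for tmax to reproduce. The 36 completers relate to the Cmax and AUC ratios.

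**Step 1: examples that need no distribution (n = 36).**

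*Hidden shift.* Fasting to fed, in hours:
- 24→24 (1 subject), 24→36 (12), 36→48 (4)
- 48→48 (5), 48→72 (4), 72→120 (9), 120→120 (1)

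The 18th and 19th ordered values are 48 h in both conditions. Minimum/median/maximum is 24/48/120 h both fasting and fed. Yet 12 + 4 + 4 + 9 = 29 subjects peak later when fed and none earlier. The paired differences are 0 (7 subjects), 12 (16), 24 (4) and 48 h (9), with median 12 h.

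*Invented shift.* Fasting: 48 h in 19 subjects and 72 h in 17. Two subjects move from 48 to 72 h and 34 do not change. The medians become 48 and 72 h, while the median paired difference is 0.

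**Step 2: how often this could happen.** Assumptions, none from the documents: log-normal tmax, between- and within-subject log-SD both 0.3 or both 0.4, each value read at the nearest scheduled time on the log scale, 18 + 18 subjects, at least 1,500 trials per case. With no true delay:

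| True median tmax | Trials in which the two medians differ |
|---|---|
| 20 h | about 0-2% |
| 24 h | 2-11% |
| 72 h | 3-15% |
| 30, 60 or 96 h | nearly half |

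The pattern follows the rounding boundaries: √(24×36) = 29.4 h, √(48×72) = 58.8 h and √(72×120) = 93.0 h. Medians near a boundary are unstable; those well inside a cell are not. At 30 h the gap reaches 12 h or more in 26-28% of trials.

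With a true 1.5-fold delay, the medians are identical in 34-38% of trials from 20 h, where the fed median is again 30 h. From 24, 36 or 48 h they are identical in only 1-5%.

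A second model (log-SD 0.25, nearest time on the arithmetic scale, no delay) agrees. The medians differ by at least 12 h in 51% of trials at 60 h and 50% at 96 h, but in 3% at 36 h and 2% at 72 h.

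**Step 3: the paired alternative.** For each subject take (Period 2 − Period 1)/2. Its expectation is (δ + π)/2 in the fasting-first group and (−δ + π)/2 in the fed-first group, where δ is the food shift and π the period effect. The difference between groups is δ, so period cancels. The Hodges-Lehmann estimate is the median of 18 × 18 = 324 between-group differences. The approximate 90% limits are the ordered values at ranks

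162 − 1.645 × √(324 × 37/12) = 162 − 52.0 ≈ 110, and 325 − 110 = 215.

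Under the Step 2 assumptions:
- Root mean square error against the true shift, Hodges-Lehmann versus difference of medians: 2.7 versus 6.1 h (20 h, 1.5-fold) and 7.4 versus 21.9 h (60 h, 1.5-fold).
- From 20 h with a 1.5-fold delay, the interval excludes zero in 85-95% of trials.
- With no delay, it falsely shows a delay in 1% or less at 30 h and under 2% at 60 h.
- Coverage of the true delay falls below 90% in some cases: 61-82% (12 h, 1.5-fold) and 80-84% (20 h, 1.25-fold). In the second of these it excludes zero in only about 25% of trials.

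**The case against.** Protocol and SAP agree in treating all secondary PK parameters descriptively. Half-life and clearance get no contrast either, and no conclusion or decision rule rests on tmax. That stands: this is a consistent choice, not an error or a contradiction.

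A reader might infer that the pairing is lost and the delay cannot be seen. The documents do not support that. PKT-2.1 prints individual values, so pairs can be matched by hand, and PKF-4.1 shows individual test-versus-reference profiles. What is missing is a pre-specified estimate with an interval. Even that can be said only of the readable text, since SAP section 13 and several PKT/PKF entries are redacted.

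A reader might also infer that the two medians will mislead. The high percentages arise when a condition median lies near a rounding boundary. Neither the expected tmax nor the sampling rationale is readable, so nobody can say from the documents which row of the table applies.

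Nor does pairing repair the grid. In the second model, a true 12 h delay from 72 h gives a zero difference of medians in 93% of trials, and the simple median paired difference is still zero in 75%. Finally, the documents name no tmax delay that would matter. The 10 h delay simulated from 20 h is 10/168 = 6% of a weekly interval.

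**Conclusion.** The point holds in a limited form. In the readable text tmax has no within-subject, period-adjusted food estimate or interval, and the two planned medians may hide or exaggerate a shift. The size ranges from negligible to about half of trials, and it rests on assumed log-normal tmax distributions and on a true tmax that the documents do not show. The Step 1 examples need no such assumption, but they show only what is possible, not how likely it is.

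Pairing largely removes invented shifts and only partly recovers hidden ones. The Cmax and AUC analyses and the sample size are untouched. This is a cheap improvement to a descriptive secondary analysis, not a flaw in the trial's main result.

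**What to change.** In SAP 10.2 2) b), add for brexpiprazole tmax, using actual sampling times, the Hodges-Lehmann fed-minus-fasting difference from halved period differences compared between the two sequence groups, with a 90% interval. Show it as a descriptive row alongside PKT-3, with the number of subjects who have tmax in both periods. Keep the existing minimum, median and maximum.

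Add a footnote that the interval is approximate, that ties and the sampling interval around tmax limit its resolution, and that it may under-cover the true delay. Attach no decision rule.

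The cost is one or two SAP sentences, one table row and its programming. No new data, samples or subjects are needed. The downside is that an interval with a 90% label may look more precise than the grid allows, which is why the footnote matters.
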